374 Inventory Severity subscale)¹⁴ and reply paid envelope. The letter of invitation will be printed on the
375 clinic letterhead and will be signed by patients' treating clinician, preferably as original signatures
376 but alternatively using electronic signatures with their permission. Participants will be able to opt
377 into the study by returning the signed consent form and participation card to the researchers by
378 reply paid mail or to decline study participation by returning the participation card, or by phone or
379 email. Potential participants will be asked to indicate whether they meet each of the inclusion
380 criteria (e.g. own a compatible Smartphone etc.) and to specify on their participation card how they
381 would like to receive the study dermatoscope and questionnaires reminders (on Text SMS or
382 email). Participants who do not return their consent form or participation card within two weeks will
383 be contacted via telephone by the research staff. If the participant does not return their consent
384 form after this telephone call, no further contact will be made. Participants that do not respond will
385 be recorded as screen fails. The clinic staff will be informed which patients have agreed to
386 participate in the study.

387
388 Consenting participants will then be sent a baseline package in the mail.

389 8.2. Stratification and Randomisation

390 Patients will be stratified by the following factors:

- 391 • AJCC Melanoma Stage (0, IA, IB, IIA, IIB/IIC)
- 392 • Sex/gender (male/female)
- 393 • Age group (18–40, 40–60, 60+)
- 394 • Clinic type (GP clinic/specialist clinic)

395
396

397 Patients will be randomised 1:1 taking into account the above listed stratification factors using a
398 randomisation to one of two study arms:

399 Randomisation will be performed using the offsite randomisation service provided by the NHMRC
400 Clinical Trials Centre, The University of Sydney, thus ensuring allocation concealment. The
401 research coordinator will call the NHMRC Clinical Trials Centre (using their telephone
402 randomisation service) to randomise the patient once a consent form and the baseline
403 questionnaire has been received. Consenting patients who meet all inclusion/exclusion criteria will
404 be randomised in a ratio of 1:1 to the intervention or usual care.

405
406

Full instructions on how to randomise patients are described in the Operations Manual.

407 8.3. Interventions/ Groups

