408 Participants allocated to the intervention will receive:

- 409 • An educational booklet 'Your guide to early melanoma',
- 410 • Web-based ASICA skin checker log-in. The web-based ASICA skin checker combines
411 instructional videos, guided total skin self-examination and electronic reporting,¹⁵
- 412 • A dermatoscope to attach to their phone similar to that reported in *Manahan et al.*¹⁶.
- 413 • Detailed written instructions on how to use the smartphone App and dermatoscope.

- 414 • Video outlining how to use the dermatoscope and associated App/online submission
 415 platform.
 416 • Email or SMS text reminders every 2 months to perform SSE.
 417 • Teledermoscopy: participants are required to take dermoscopic images of at least 3 lesions
 418 and up to 9 lesions on each SSE, including all lesions that concern them, and submit these
 419 through the smartphone App. They are also required to enter a text description of the results
 420 of SSE for each part of the body and submit this through the web-based ASICA skin
 421 checker. Both dermoscopic images and text reports will be sent securely to one of the study
 422 dermatologists, who will undertake teledermatology review within 3 days and feedback the
 423 results to the participant.
 424 • Unscheduled visits as needed in addition to those prompted through Teledermatology.
 425 • Scheduled visits as per treating clinician.
 426

427 Those allocated to the control arm will receive:

- 428 • An educational booklet 'Your guide to early melanoma';
 429 • Unscheduled visits as needed
 430 • Scheduled visits as per treating clinician
 431

432 All participants will receive two study questionnaires; one at baseline and one at 6 months.
 433

434 **8.4. Blinding**

435 Blinding of participants, site staff and treating clinicians will not be possible in this trial. Where
 436 possible, outcome assessment will be done masked to study group allocation.
 437

438 **8.5. Duration of treatment/ Study**

439 Unless the study is closed prematurely, it will proceed to the pre-defined accrual target. Following
 440 announcement of closure to recruitment by the research team, no further enrolment will be
 441 possible. It is anticipated, based on estimates from individual sites that the accrual target will be
 442 reached over a period of 6 months. Each participant will be followed up for 6 months. The timeline
 443 below provides an outline of anticipated study milestones:
 444
 445

Timeline	2017	2018	2019	2020

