607 • is a congenital anomaly/birth defect;
608 • is a grade 4 (NCI CTCAE v4.0) toxicity;

609 **and**

- 610 • could be related to the device and/or software
 611 The term “life threatening” in the definition of SAE refers to an event in which the participant was at
 612 risk of death at the time of the event; it does not refer to an event which, hypothetically, might have
 613 caused death if it were more severe.

614

615 **SAE Reporting**

616 All relevant and subsequent information relating to each reported SAE must be submitted on the
 617 CRF, along with any available source documentation, to the Trial Coordinating Centre. This must
 618 be completed within 24 hours of the site becoming aware of the event and all SAE CRFs require
 619 the signature of the Principal Investigator.

620

621 **SAE Reporting Timelines**

Type	Timeframe
Initial SAE Report	The site must submit the original SAE Form to the Trial Coordinating Centre within 24 hours of becoming aware of a trial participant experiencing an SAE. Please provide copies of relevant source documents if available. Should the site have any questions please immediately contact the Trial Coordinating Centre for assistance.
Updated Report	The site should provide any updates to the Trial Coordinating Centre as soon as possible. Please use the original SAE Form, and use additional Forms if more space is required. Please provide copies of all relevant source documents if available.
Completed Report	Once the event has resolved or if the participant has died, using the original SAE Form(s), the site should provide the complete report to the Trial Coordinating Centre as soon as possible. This must include relevant source documents.

622

623 All SAEs will be reviewed by the Study Chair and also summarised for review by the Data Safety
 624 Management Committee.

625

626 SAEs will be reported as per the local Ethics Committee (EC)/Research Governance Officer (RGO), in
 627 accordance with international and local laws and regulations.

628

629 Should any trial site have any questions they will immediately contact the Trial Coordinating Centre for
 630 assistance.

631 **12. Outcomes/ Measures**632 **12.1. Primary outcome**

633 **(M1)** The primary outcome is the **proportion of patients who are invited to participate who are**
 634 **finally randomised into the trial.**

635 **12.2. Secondary outcomes**636 **(M2) Skin –Self Examination (SSE) including:**

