700 The proportion of patients who are randomised into the trial will be estimated using the number of
701 contacted patients as the denominator. The Wilson (score) method will be used to estimate the
702 confidence interval for this proportion to assess the best and worst case scenarios supported by the
703 pilot study data. We will investigate and describe any groups that had low participation rates in our
704 pilot study.

705

706

707 13.4.2. Statistical analysis for secondary endpoints

708 We will use a chi-squared test to investigate the difference in proportion undertaking regular skin
709 self-examination between the intervention arm and the usual care arm. A t-test will be used to
710 compare fear of new or recurrent melanoma severity at 6 months between the intervention and
711 usual care group. We will report any estimated differences (either proportions or means) with
712 appropriate confidence intervals as the power for these comparisons will be limited.

713

714 13.5. Secondary analyses**715 *Teledermatology Repeatability Study***

716 Sub-study to assess Dermatologist diagnostic agreement of electronic text reports and images
717 collected during the trial.

718 We will assess inter-rater agreement across three dermatologists, reporting on prospectively
719 collected Teledermatology materials. After close-out of the trial, three dermatologists (CIs [name],
720 [name] and [name]) will independently review all electronic reports and images of patient detected
721 lesions that they did not report on during the trial. All three dermatologists will report their results
722 blinded to those of the other two dermatologists and to any other clinical information apart from that
723 received during the Teledermatology (age and sex of patient and the text report describing the
724 lesion where this was provided).

725 Agreement across the following broad clinical diagnostic categories will be calculated:

- 726 • No concern today [i.e. benign]
- 727 • Follow up photo [i.e. low probability of melanoma/NMSC]
- 728 • Clinical Exam [i.e. intermediate probability of melanoma/NMSC]
- 729 • Biopsy/excision [i.e. high probability of melanoma/NMSC]
- 730 • Only one category per patient episode allowed, where teledermatologist makes more than
731 one diagnosis, most severe diagnostic category used.

732 We will construct cross-classification tables to separately compare inter-rater reliability for text

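### Does the primary proportion need a rule for invitations still open when recruitment closes?

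*Combined protocol and SAP*

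**What the plan says.** Section 12.1 defines the primary outcome among invited patients as those "finally randomised into the trial". Section 13.4.1 divides by "contacted patients as the denominator. The Wilson (score) method will be used to estimate the" interval, and gives the interval's purpose: "confidence interval for this proportion to assess the best and worst case scenarios supported by the" pilot data.

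On recruitment, section 8.5 says that, barring premature closure, "it will proceed to the pre-defined accrual target", and that this target should be "reached over a period of 6 months". Enrolment ends with the "announcement of closure to recruitment by the research team, no further enrolment will be" possible. The target is 100 patients, 50 per arm (section 3).

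Section 8.1 sets the reply process: "Participants who do not return their consent form or participation card within two weeks will" receive a telephone call. If no consent form is returned, "form after this telephone call, no further contact will be made", and non-responders are logged as screen fails. Section 8.2 allows randomisation only when both the consent form and the baseline questionnaire are in.

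No section gives a last invitation date, a time limit for replies after the call, or a rule for invitations pending at closure.

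**The concern.** There is always some delay between contact and randomisation, because the patient must return two documents first. Anyone contacted just before closure has had less chance to be randomised than someone contacted in the first month. Read literally, section 13.4.1 still counts that person in the denominator, and section 8.5 may prevent them from ever entering the numerator. The result would be a proportion that is too low. The Wilson interval reflects sampling error only, so it would move down with the estimate and would not warn of the problem.

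This pilot exists to help plan a larger trial (section 5.2). An uptake estimate that is too low would lead planners to budget for more invitations than needed, and would make the lower end of the interval look worse than the data warrant.

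**Working it through.** **Inputs.** Uptake of 30% (13.1), 100 randomised (3 and 13.1), accrual over 6 months, taken as 26 weeks (8.5), and a two-week reply trigger followed by one call (8.1). The lag from invitation to randomisation is not given, so it is an assumption: a mean of *L* = 1 to 2 weeks, with 0.5 and 4 weeks as outer values.

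**The plan's own figure.** Section 13.1 claims a margin of error below 10%. The Wald half-width is 1.96 × √(0.3 × 0.7 / n):
- n = 100: 8.98 points (Wilson 8.84).
- n = 100 / 0.30 = 333 contacted: 4.92 points (Wilson 4.90; interval for 100/333 is 25.4% to 35.2%).

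The claim holds on either reading.

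**Size of the possible shift.** Suppose invitations go out evenly until the 100th randomisation and pending patients are then excluded from randomisation. The weekly rate is 333.3 / 26 = 12.8, and the expected estimate is about 100 / (333.3 + 12.8 × *L*). With 12-month accrual the rate is 333.3 / 52 = 6.4.

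| Mean lag *L* | 6-month accrual | Shift (points) | 12-month accrual | Shift (points) |
|---|---|---|---|---|
| 0.5 weeks | 29.4% | -0.6 | 29.7% | -0.3 |
| 1 week | 28.9% | -1.1 | 29.4% | -0.6 |
| 1.5 weeks | 28.4% | -1.6 | 29.2% | -0.8 |
| 2 weeks | 27.9% | -2.1 | 28.9% | -1.1 |
| 4 weeks | 26.0% | -4.0 | 27.9% | -2.1 |

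**Simulation.** Stopping at a fixed number of randomised patients raises the estimate by about 0.2 points even without any lag, which offsets part of the shift. Simulated net shifts at the 6-month pace, with the share of Wilson intervals that contain the true 30%:
- lag uniform on 0 to 2 weeks (mean 1): -0.9 points, coverage 93.9%;
- 0 to 3 weeks (mean 1.5): -1.5 points, 90.8%;
- 0 to 4 weeks (mean 2): -2.0 points, 87.7%;
- 2 to 4 weeks (mean 3, a pessimistic case): -3.0 points, 76.7%.

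At the 12-month pace, mean lags of 1 to 2 weeks give net shifts of about -0.4 to -0.9 points, with coverage of 94% to 95%.

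**How the pending invitations might be handled.** In the same simulation at the 6-month pace:
- following every open invitation to its outcome leaves about +0.2 points, which is the stopping effect alone;
- counting only invitations issued at least 4 weeks before closure, with lags of up to 4 weeks, leaves about 0.0;
- discarding open invitations gives +1.0 to +2.9 points if non-responders are taken as open for 4 weeks, because they stay open longest.

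The first option would randomise about 0.30 × 12.8 × *L* further patients: 3.8 at *L* = 1 and 7.7 at *L* = 2.

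**Against the precision of the study.** Net shifts of 0.9 and 2.0 points are 0.9 / 4.9 = 18% and 2.0 / 4.9 = 41% of the Wilson half-width. In invitations for a later trial, the excess is 30 / 28.9 = 1.04 to 30 / 27.9 = 1.08, or 4% to 8%. Sampling error alone is 4.9 / 30 = 16% either way. The interval's lower limit would be 24.4% (100/346) or 23.5% (100/359) instead of 25.4%.

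**The case for a change.** The strongest argument for amending the plan is that this is the sole primary outcome, and that counting, dropping or following up the pending invitations gives different answers in different directions. Screen-fail status in 8.1 does not settle it, since it describes patients who have been through the reminder process, and applying it to patients cut off by closure would produce the downward shift. The general statement on missing data in 13.6 does not help either. A larger sample collected in the same way would not reveal the shift, and at a mean lag of 2 weeks coverage falls to about 88%. A few lines of text would remove the ambiguity.

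The gap and the arithmetic stand. What does not stand is that the plan, as written, produces this bias. Three things must happen together: inviting continues to the last day, closure falls at the 100th randomisation, and pending patients are then refused. Section 8.5 ties closure to an announcement whose date the team sets, so inviting can stop first. Enrolment (8.1) and randomisation (8.2) are described separately, so the ban on further enrolment need not exclude someone who has consented and whose questionnaire is awaited. The wording of 12.1 points to each patient's final status. The lag could also be short, because 8.1 allows the package, including the baseline questionnaire, to be handed over in person. The timeline table in 8.5, although poorly preserved, appears to mark recruitment in two calendar years. That would be compatible with slower accrual and a smaller shift, but does not establish it.

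**Conclusion.** No change to the plan follows. The documents are silent on invitations pending at closure, and under one unfavourable way of running recruitment the primary proportion would come out too low. At 30% uptake and a mean lag of 1 to 2 weeks, the net shift is about -0.9 to -2.0 points over 6 months of accrual or -0.4 to -0.9 over 12, and zero if invitations resolve first. The lag is an assumption. A 4-week mean lag would give -4.0 points at the 6-month pace by the simple formula, still inside the 4.9-point half-width.

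No figure in the documents is wrong. The plan sets no progression threshold, so no stated decision would change, and the error would make the pilot look slightly less feasible than it is. Letting pending invitations resolve before calculating the proportion is ordinary practice, is consistent with the outcome definition in 12.1, and leaves the feasibility conclusion sound.

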336 We will conduct a qualitative sub-study to understand patients' and clinicians' acceptability and
337 satisfaction with the intervention and explore components which may need to be changed. The
338 qualitative evaluation will be in the form of phone or face to face interviews at the end of the 6
339 month follow-up.
340

341 7. Study population

342 We will recruit adult participants who have been treated for a first primary melanoma, stage 0/I/II,
343 and who are undergoing regular melanoma follow-up at recruiting melanoma and skin cancer
344 clinics in NSW.
345

346 This pilot study aims to recruit 100 patients from the Melanoma Institute Australia (MIA) and Royal
347 Prince Alfred Hospital (RPAH) (specialist treatment centres) and the Newcastle Skin Check clinic
348 (GP run clinic). Recruitment will be done over six months.
349

350 7.1. Inclusion Criteria

- 351 • Patients treated for stage 0/I/II melanoma who are attending regular melanoma follow-up as
352 indicated by scheduled or recommended visit within next 12 months.
353 • Are able to self-examine;
354 • Have a suitable study partner (spouse, partner, family member, friend) to help with self-
355 examination
356 • Own a compatible Smartphone (and have access to Wifi / email / SMS text messaging);
357 • Are able to give informed consent;
358 • Have sufficient English language skills to read the materials and complete the
359 questionnaires;
360 • Aged 18+ years old.

361 7.2. Exclusion Criteria

- 362 • unable to perform self-examination
363 • Patient who currently or previously have had stage III/IV melanoma
364 • Patients with a known past or current diagnosis of cognitive impairment

365 8. Study procedures

366 8.1. Enrolment procedure

367 All patients treated for localised melanoma who are attending regular follow-up, will be identified in
368 clinic by the clinician. The potential participant will be contacted by a research coordinator who will
369 explain the study and give the patient an invitation package either in person or by mail. The initial
370 study invitation package includes: Study Invitation Letter, Participant Information Sheet, Consent
371 Form, Participation Card, Baseline Questionnaire (to measure demographics, knowledge, attitudes
372 and confidence on self-examination and smartphone Apps, and their baseline level of fear of new
373 or recurrent melanoma (using a melanoma specific version of the Fear of Cancer Recurrence

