8.6. Asses

464 **ment schedule and follow up**

465 *Follow-up:* All participants will be complete a questionnaire at baseline (T0: prior to randomisation)
466 and 6 months (T1) follow-up which they can complete in hard copy or online. Data will be extracted
467 from clinic databases for 6 months from randomisation, including surgical procedures and
468 histopathology.

469 **8.6.1. Follow-up questionnaire (T1): 6 months**

470 Participants will be mailed the first follow-up questionnaire (or provided with a link to the online
471 survey via email) 6 months after randomisation. If participants do not return their completed
472 questionnaire within 1 week of postage or email, the researchers will contact the participant by
473 SMS text and/or email (according to the participant's preferred method of contact) as a reminder
474 about the study. The researchers will remind the participant 5 times. If there are delays with the
475 return of the questionnaire, and the participant appears to have problems completing the
476 questionnaire on paper or online, the research coordinator will offer to administer the questionnaire
477 over the telephone.
478

479 **8.6.2. End of study.**

480 Measurement of outcomes will be at 6 months (T1questionnaire) for evaluation of intervention
481 effects. If a patient has not completed the schedule of follow up visits, further follow up of outcomes
482 will continue up to a maximum of 12 months. If a patient withdraws consent to participate, a Study
483 Discontinuation Form will be completed (see below).
484

485 Similarly, if a patient dies, a Study Discontinuation Form will be completed and a copy of the death
486 certificate or discharge summary provided. Reason for death, melanoma/skin cancer related or not,
487 will be considered in the final analysis.
488

489 **8.6.3. Withdrawal and Lost to Follow up**

490 Participation in this study is voluntary; patients are able to withdraw at any time.
491

492 If a patient decides to stop their follow-up visits but is willing to keep in contact via telephone, their
493 health status will be periodically ascertained by way of phone contact with their general practitioner
494 or by direct phone contact with the patient.
495

496 For those patients who want to have no further contact, all correspondence regarding the trial will
497 be discontinued. A Study Discontinuation Form is to be completed at the last study visit the patient

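### Fear of recurrence is compared by an unadjusted 6-month t-test, although the baseline score is collected before randomisation and allocation is stratified

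*Combined protocol and SAP*

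**What the plan says.** Section 13.4.2 states that a t-test will be used to "compare fear of new or recurrent melanoma severity at 6 months between the intervention and" the usual-care group. It names no covariate. It then says that differences will be reported with "appropriate confidence intervals as the power for these comparisons will be limited".

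Four other places bear on this:

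- **Section 8.1** lists the contents of the baseline questionnaire, among them patients' knowledge, attitudes and confidence "and their baseline level of fear of new" or recurrent melanoma, measured with a melanoma-specific version of the Fear of Cancer Recurrence Inventory severity subscale. Section 12.2 (M3) names the same subscale as the outcome.
- **Section 8.2** allows the randomisation call only after the consent form and baseline questionnaire have arrived. Section 8.6 places the baseline questionnaire before randomisation for all participants, and section 10.3 sends study packages only after it has been received.
- **Section 8.2** also says "Patients will be stratified by the following factors": AJCC stage (five levels), sex (two), age group (three) and clinic type (two).
- **Section 12.3** lists potential confounders to be collected but ties them to no model. Section 13.6, on missing data, does not mention covariates.

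No section adjusts any comparison for a baseline score or a stratification factor.

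**The concern.** The best available predictor of a questionnaire score at 6 months is usually the same score at baseline. The trial collects it before allocation and then leaves it out of the comparison. Two consequences follow, both aspects of the same loss of precision:

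- Outcome variance that the baseline score could explain stays in the residual, so the interval is wider than the data require.
- A chance difference in baseline fear between arms of about 50 carries over into the 6-month difference in proportion to the correlation, with no correction.

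Leaving out the stratification factors adds to this. If they predict the outcome, balancing on them reduces the true sampling variance, but an unadjusted standard error does not reflect that reduction.

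Reducing fear of new or recurrent melanoma is a stated secondary aim (section 6.1, aim 3). It is also one of only two endpoints given a named test in 13.4.2. Section 5.2 says the pilot will support planning of a larger trial in which better psychological outcomes are expected. A noisier estimate is less useful for that purpose.

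**Working it through.** **The plan's own precision figure.** The only one concerns the primary outcome: a margin of error below 10%, assuming 30% recruited (section 13.1). With 100 as denominator, 1.96 × √(0.30 × 0.70 / 100) = 9.0%, and the Wilson interval is 21.9% to 39.6%. With 333 contacted (100 / 0.30), the margin is 4.9%. The figure reproduces on either reading. No precision or power figure is given for fear of recurrence.

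**Inputs.** n = 50 per arm (section 13.1). Assumptions, because the documents give no values: two-sided α = 0.05; baseline-to-6-month correlation r from 0.3 to 0.7; an illustrative true difference of 0.5 SD. Results are in units of the 6-month SD.

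**Formulas.**

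- Residual variance factor after adjusting for baseline: 1 − r².
- SE of the difference: √(1 − r²) × √(2/n), with √(2/50) = 0.20.
- Interval width relative to the t-test: √(1 − r²).
- Equivalent unadjusted n per arm: 50 / (1 − r²).
- Power: non-central t with non-centrality 0.5 / SE, on 98 df for the t-test and 97 df with one covariate. For example, r = 0 gives 0.5 / 0.20 = 2.50, and r = 0.5 gives 0.5 / (0.866 × 0.20) = 2.89.
- Detectable difference: the value giving 80% power under the same distribution.

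| Analysis | 1 − r² | Relative CI width | 95% CI half-width (SD) | Power for 0.5 SD | Detectable at 80% (SD) | Equivalent n per arm |
|---|---|---|---|---|---|---|
| t-test | 1.00 | 1.00 | 0.397 | 69.7% | 0.566 | 50 |
| ANCOVA, r = 0.3 | 0.91 | 0.95 | 0.381 | 73.7% | 0.540 | 55 |
| ANCOVA, r = 0.5 | 0.75 | 0.87 | 0.346 | 81.5% | 0.490 | 67 |
| ANCOVA, r = 0.6 | 0.64 | 0.80 | 0.319 | 87.2% | 0.453 | 78 |
| ANCOVA, r = 0.7 | 0.51 | 0.71 | 0.285 | 93.4% | 0.404 | 98 |

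The half-widths include a small allowance for estimating the covariate effect. Their ratios are therefore slightly above the relative widths shown.

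**Loss to follow-up.** The plan gives no rate. Assuming 10% loss (45 per arm), power goes from 65.0% to 77.3% at r = 0.5. Assuming 20% loss (40 per arm), it goes from 59.8% to 72.2%.

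**Cost of adding the stratification factors.** As main effects they use 4 + 1 + 2 + 1 = 8 df. At 50 per arm this costs about 0.1 percentage point of power, before any gain from their prognostic value. Full cross-classification is not workable: 5 × 2 × 3 × 2 = 60 cells for 100 participants.

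**Chance imbalance.** The baseline difference between arms has SE 0.20 SD, so about one trial in 20 has an imbalance above 1.96 × 0.20 = 0.39 SD. At r = 0.5 to 0.7 that moves the unadjusted 6-month difference by 0.20 to 0.27 SD (0.39 × r).

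**The case against.** The t-test is valid and unbiased under randomisation, and its interval already allows for chance imbalance, so nothing here is an error. Fear of recurrence is a secondary outcome in a feasibility pilot sized on the recruitment proportion, and the plan openly says power is limited. It sets no target difference for fear and does not say that this estimate will size the larger trial. The gain depends on a correlation that the documents do not give, for a modified instrument. At r = 0.3 the interval narrows by only about 5% and power rises from 70% to 74%. The stratification argument needs the factors to predict fear, which nothing in the documents shows, and none of the quoted gain comes from them. For confidence, knowledge and attitudes, 13.4.2 names no test to replace.

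All of this is fair and limits the weight of the point: it concerns efficiency, the primary outcome is untouched, and the size is conditional on r. It does not justify leaving out the baseline score. The covariate is already in hand, adjustment costs almost nothing if r is low, and interval width is the criterion the plan itself adopts.

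One further limit is that Table 1 mentions only the consent and participation card as returned before randomisation, and section 8.1 mails a baseline package after consent. Sections 8.2, 8.6 and 10.3 nevertheless require the questionnaire first, so baseline scores should exist for everyone apart from incomplete items.

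**Conclusion.** The concern holds, as a recommended improvement and not as a flaw that invalidates the analysis. The plan compares 6-month fear scores without using a baseline score it requires before randomisation or the factors it stratifies on, and no other section makes up for this. If r is 0.5 to 0.7, the t-test interval is wider than it need be: adjustment would narrow it by 13% to 29% and lower the detectable difference from 0.57 SD to between 0.49 and 0.40 SD. If r is 0.3, the gain is small. These figures assume 50 analysed per arm and take no credit for the stratification factors, whose contribution cannot be quantified from the documents.

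**What to change.** In 13.4.2, replace the t-test for fear of recurrence with a linear model (ANCOVA) of the 6-month severity score on arm, baseline severity score and the randomisation factors as main effects. Report the adjusted mean difference with its 95% confidence interval, and keep the unadjusted difference as a sensitivity analysis.

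Details to settle in the same edit:

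- Enter age as continuous, since the bands in section 8.2 overlap at 40 and 60.
- State in advance how sparse stage levels will be merged and how incomplete baseline items will be handled.
- Do not substitute a change score. Its variance factor is 2(1 − r), which gives no gain at r = 0.5 and is worse than the plain t-test below that.
- Use the same model for the confidence, knowledge and attitude measures collected at baseline, where they are scored as continuous scales. Section 13.4.2 currently gives them no method.
- Report the observed baseline-to-6-month correlation, which the larger trial can use in its sample-size calculation.

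The cost is one sentence for the model plus the short rules above. No new data, visits or participants are needed.
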